8.7 EoS (Follow-up) Procedures/Visit 7 (Day 84)

On completion of the study (Visit 7/Day 84±4 days), all assessments per Table 1 should be performed.

All subjects whether completing the treatment or who have withdrawn prematurely, will be followed up for 4 weeks (28±4 days after EoT) after their last administration of IMP to collect, at a minimum, any potential new AEs and concomitant medications (or other endpoints as defined in Table 1). If the Investigator has not seen the subject at in-hospital visit at the end of the reporting period, the Investigator must attempt 3 telephone calls to the subject, and if there is no response, the source documents and the eCRF should document the reason for study discontinuation as "lost to follow-up".

The following activities will be performed at Visit V7:

- Perform physical examination. Body systems to be assessed include general appearance, head (eyes, ears, nose, and throat), cardiovascular, respiratory, abdominal, musculoskeletal, neurological, lymph nodes, and skin
- Assess vital signs, e.g., systolic blood pressure, diastolic blood pressure, and pulse, after subject has rested for at least 5 minutes
- Perform a single 12-lead ECG
- Assess SAEs/AEs
- Assess changes/additions to concomitant medications
- Prepare RBC blood smear (local laboratory) to assess for sickle cells (central laboratory)
- Urine pregnancy test (only in females of childbearing potential). Positive urine pregnancy test results need to be confirmed using a serum beta-hCG test (local laboratory assessment)
- Collect urinalysis samples (urinary dipstick test) for central laboratory assessment of pH, protein, glucose, ketone, RBCs, and WBCs
- Collect samples for central laboratory assessment of:
 - Haematology panel/RBC indices
 - Serum chemistry panel
 - Haemolysis markers
 - Endothelial inflammation/dysfunction markers

- Total serum iron, serum ferritin, serum transferrin, calculated TSAT, hepcidin, and erythropoietin
- Record VOC episodes (number of events and pain intensity (NRS: 0-10) compared to historical VOC episodes). Assess visceral infarctions as per standard of care

8.8 Allowed Adaptations for Assessments During Site Visits

To provide some flexibility for specific assessments during the site visits, which can be performed post-dose instead of pre-dose as required per the current protocol, the following assessments must be performed before VIT-2763 morning dose administration at the site:

- Collection of AEs and changes/additions made to concomitant medications
- Vital signs assessment
- Pre-dose single 12-lead ECG
- Pre-dose PK blood sample
- Blood sample to assess Hb to confirm eligibility at Visit V2 to assess whether the study therapy can be continued (Visits V2–V5) (local laboratory)
- Blood sample for pre-dose iron-related parameters

After Visit V2, the following assessments can also be performed post VIT-2763 morning dose administration at the site:

- Physical examination
- Body weight recording
- RBC blood smear (local laboratory) to assess for sickling cells (central laboratory)
- Urinalysis sample for central laboratory
- Blood sample for haematology panel/RBC indices (sample for central laboratory)
- Blood sample for serum chemistry panel (sample for central laboratory)
- Blood sample for haemolysis markers
- Blood sample for inflammatory endothelial markers
- VOC episodes recording and visceral infarction as per standard of care assessment
- ASCQ-Me Questionnaire collection

Other assessments not mentioned within this list are to be followed as per protocol.

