Collect, dispense, and inform subjects on ASCQ-Me questionnaires ⁽¹⁶⁾	X	X	X	X	X	X	
IMP accountability			X	X	X	X	

¹ Any outstanding eligibility criteria (see Section 5.2 and Section 5.3) not available during screening to be available before randomisation.

² Body systems to be assessed include general appearance, head (eyes, ears, nose, and throat), cardiovascular, respiratory, abdominal, musculoskeletal, neurological, lymph nodes, and skin.

³ Seated systolic and diastolic blood pressure, and pulse, after subject has rested for at least 5 minutes, pre-dose (trough).

⁴ A single 12-lead ECG to be performed at pre-dose (trough) and 2 hours (±30 minutes) post-morning dose.

Only in females of childbearing potential. Positive urine pregnancy test results need to be confirmed using a serum beta-hCG test.

⁶ Only in females of childbearing potential.

⁷ Only if genetic diagnosis records do not exist or are unavailable.

⁸ Urinary dipstick including pH, protein, glucose, ketone, RBCs, and WBCs. Quantitative measurement only if positive dipstick. Urinalysis includes also (at Visits V1, V2, V4, and V6) urinary microalbumin, creatinine, and microalbumin/creatinine ratio (spot sample, morning void).

- 9 Haematology panel/RBC indices sampled at pre-dose (trough) include: Hb, reticulocytes (abs, %), RBC count, Hct, MCH, MCV, MCHC, RDW, % hypochromic RBC, CHCM, WBC, neutrophils (abs, %), lymphocytes (abs, %), monocytes (abs, %), eosinophils (abs, %), basophils (abs, %), and platelets. At screening/Visit V1, only Hb and reticulocytes will be assessed. At screening, the optional SCD genotyping test can be included.
- 10 Serum chemistry sampled at pre-dose (trough) includes calcium, sodium, magnesium, potassium, phosphorus, chloride, bicarbonate, blood urea nitrogen, uric acid, creatinine kinase, creatinine, folic acid, albumin, total protein, globulin (calculated), alanine transaminase, aspartate transaminase, alkaline phosphatase, glucose, triglycerides, and cholesterol.
- 11 Haemolysis markers sampled at pre-dose (trough) include LDH, free haptoglobin, and direct/total bilirubin (indirectly calculated).
- 12 Endothelial inflammation/dysfunction markers sampled at pre-dose (trough) include hsCRP, IL-1, IL-6, TNF-alpha, sP-selectin, sVCAM-1, xanthine oxidase, and endothelin-1.

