- 13 Iron-related parameters/markers of erythropoiesis sampled at pre-dose and 2 hours post-morning dose include total serum iron, serum ferritin, transferrin, TSAT, hepcidin, and erythropoietin. At Visit V1, serum ferritin, and TSAT will be sampled for exclusion criteria only.
- 14 PK samples are collected on Visit V4 at pre-dose, and 2 hours (±15 minutes), 4 hours (±30 minutes), and 6 hours (±30 minutes) post-dose.
- 15 At Visit V2, the subject will be asked for VOC episodes within the last 8 weeks. At Visits V3, V4, V5, and V6, the subject will be asked for VOC episodes (number of events and pain intensity (NRS: 0-10) compared to historical VOC episodes) since previous visits. Visceral infarctions will be assessed as per standard of care.
- 16 For more details see the respective visit in Section 8.

Notes: abs=Absolute; ASCQ-Me=Adult Sickle Cell Quality of Life Measurement System; C=Central laboratory assessment; CHCM=Corpuscular Hb concentration mean; ECG=Electrocardiogram; EoS=End of study; EoT=End of treatment; ET=Early termination; Hb=Haemoglobin; HbsAg=Hepatitis B surface antigen; HBV=Hepatitis B virus; hCG=Human chorionic gonadotropin; Hct=Haematocrit; HCV=Hepatitis C virus; hsCRP=High sensitivity C-reactive protein; IL=Interleukin; IMP=Investigational medicinal product; IWRS=Interactive web response system; L=Local laboratory assessment; LDH=Lactate dehydrogenase; MCH=Mean corpuscular Hb; MCHC=Mean corpuscular Hb concentration; MCV=Mean corpuscular volume; NRS=Numerical rating scale; PK=Pharmacokinetic; RBC=Red blood cell; RDW=Red blood cell distribution width; SCD=Sickle cell disease; sP=Soluble platelet; sVCAM=Soluble vascular cell adhesion molecule; TNF=tumour necrosis factor; TSAT=Transferrin saturation; V=Visit; VOC=Vaso-occlusive crises; WBC=White blood cell.

VIT-2763-SCD-202, Version 4.0
16 March 2023
Page 22 of 108

TABLE OF CONTENTS

	Page
SIGNATURE PAGE	2
INVESTIGATOR AGREEMENT AND SIGNATURE PAGE	6
SYNOPSIS	7
TABLE OF CONTENTS	23
LIST OF TABLES	27
LIST OF FIGURES	28
LIST OF ABBREVIATIONS	

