3.4 Primary Endpoint

• Mean change from baseline in haemolysis markers as measured by reduction of indirect bilirubin after 8 weeks of treatment.

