- Urine pregnancy test (only in females of childbearing potential). Positive urine pregnancy test results need to be confirmed using a serum beta-hCG test (local laboratory assessment)
- Collect urinalysis samples for central laboratory assessment of:
 - pH, protein, glucose, ketone, RBCs, and WBCs (urinary dipstick test); quantitative measurement only if positive dipstick
 - Urinary microalbumin, creatinine, and microalbumin/creatinine ratio (spot urinary sample, morning void)

- Collect blood samples at pre-dose (trough) for central laboratory (as per Laboratory Manual) assessment of:
 - Haematology panel/RBC indices (to determine baseline value)
 - Serum chemistry panel
 - Haemolysis markers
 - Endothelial inflammation/dysfunction markers
 - Total serum iron, serum ferritin, serum transferrin, calculated TSAT, hepcidin, and erythropoietin (central laboratory assessment)
- Record number of VOC episodes within the last 8 weeks. Assess visceral infarctions as per standard of care

Randomisation and Administration of the First Dose of IMP

- Randomisation
- Dispense subject identification card
- The first dose of IMP must be administered at the site and the time of administration needs to be entered in the eCRF. The IMP total daily dose will be split depending on the subject's randomisation in 2 or 3 doses per day. If randomised to a cohort with BID treatment frequency, then dosing will occur in the morning and in the evening. If randomised to cohorts with TID treatment frequency, then dosing will occur in the morning, afternoon, and evening. For BID dosing the morning dose of the IMP will be administered with water, at least 1 hour before meals between 06:00 and 10:00 a.m. The evening dose will be administered 12 hours (±1 hour) after the morning dose 1 hour apart from meals. For TID dosing morning dose of the IMP will be administered with water, at least 1 hour before meals between 06:00 and 10:00 a.m. The afternoon dose will be administered 8 hours (±1 hour) after the morning dose 1 hour apart from meals. The evening dose will be administered 16 hours (±1 hour) after the morning dose 1 hour apart from any meals.
- Collect all 6 ASCQ-Me forms completed by subject
- Dispense IMP at site (via IWRS). Note: Only the morning dose on the visit day needs to be taken at site
- Perform a new single 12-lead ECG at 2 hours post-morning dose (±30 minutes).

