8.6 EoT (or ET) Procedures/Visit 6 (Day 56±4 Days)

On completion of treatment (or if subject is discontinued/withdrawn early), assessments for Visit 6/Day 56±4 days (per Table 1) should be performed:

- Perform physical examination. Body systems to be assessed include general appearance, head (eyes, ears, nose, and throat), cardiovascular, respiratory, abdominal, musculoskeletal, neurological, lymph nodes, and skin
- Assess vital signs, e.g., systolic blood pressure, diastolic blood pressure, and pulse, after subject has rested for at least 5 minutes
- Record body weight
- Perform a single 12-lead ECG at pre-dose

- Assess SAEs/AEs
- Assess changes/additions to concomitant medications and treatments
- Prepare RBC blood smear (local laboratory) to assess for sickle cells (central laboratory)
- Urine pregnancy test (only in females of childbearing potential). Positive urine pregnancy test results need to be confirmed using a serum beta-hCG test (local laboratory assessment)
- Collect urinalysis samples for central laboratory assessment of:
 - pH, protein, glucose, ketone, RBCs, and WBCs (urinary dipstick test); quantitative measurement only if positive dipstick
 - Urinary microalbumin, creatinine, and microalbumin/creatinine ratio (spot urinary sample, morning void)
- Collect samples at pre-dose (trough) for central laboratory assessment of:
 - Haematology panel/RBC indices
 - Serum chemistry panel
 - Haemolysis markers
 - Endothelial inflammation/dysfunction markers
 - Total serum iron, serum ferritin, serum transferrin, calculated TSAT, hepcidin, and erythropoietin (central laboratory assessment)
- IMP administered, the morning dose on the visit day needs to be taken at site
- Perform a single 12-lead ECG at 2 hours (±30 minutes) post-morning dose
- Collect samples (2 hours post-morning dose) for total serum iron, serum ferritin, serum transferrin, calculated TSAT, hepcidin, and erythropoietin (central laboratory assessment)
- Record VOC episodes (number of events and pain intensity (NRS: 0-10) compared to historical VOC episodes). Assess visceral infarctions as per standard of care
- Collect the ASCQ-Me forms completed by subject
- Perform IMP accountability

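### Protocol Section 8.8 allows the primary-endpoint blood sample to be drawn after the morning dose at Visits V3 to V6, while baseline is always pre-dose and the rest of the plan specifies trough

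*Protocol*

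**What the plan says.** The primary endpoint is "Mean change from baseline in haemolysis markers as measured by reduction of indirect bilirubin after 8 weeks of treatment" (Protocol Section 3.4). Indirect bilirubin is calculated from the haemolysis-marker sample.

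**Where trough is specified.** Protocol Table 1, footnote 11, reads "Haemolysis markers sampled at pre-dose (trough) include LDH, free haptoglobin, and direct/total bilirubin (indirectly calculated". Footnotes 9 and 10 say the same of the haematology and serum chemistry panels. Section 8.2 (baseline) has "Collect blood samples at pre-dose (trough) for central laboratory (as per Laboratory Manual) assessment of", and Section 8.6 (Visit 6) has "Collect samples at pre-dose (trough) for central laboratory assessment of". Sections 8.3 to 8.5 give the same instruction for V3 to V5. SAP Table 3, footnote 10, also specifies trough.

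**Where it is relaxed.** Section 8.8 says "After Visit V2, the following assessments can also be performed post VIT-2763 morning dose administration at the site". The list that follows includes "Blood sample for haemolysis markers" and the haematology and serum chemistry panels. The same section keeps "Blood sample for pre-dose iron-related parameters" among the items that must come before the dose.

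**What the SAP does with the values.** Baseline is the last non-missing value before first dose (Section 5.1.2). Post-baseline values are chosen by study day, and several values on the chosen day are averaged (Section 5.1.3). The primary summary is the mean change with a 95% CI by group (Section 5.7.1). None of these sections distinguishes pre-dose from post-dose haemolysis samples.

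**The concern.** The relaxation works in one direction. Follow-up samples may be post-dose, but the baseline sample cannot be. The primary summary is a within-group change from baseline, so a direct effect of a recent dose on the marker would appear in the Visit 6 value with nothing at baseline to offset it.

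Even without a drug effect, leaving the draw time to each site adds variation to a mean of about six values. A reader of the SAP would assume that all samples are trough samples, because its schedule says so, yet the protocol does not require that.

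The permission also reaches secondary endpoints: LDH, free haptoglobin and direct and total bilirubin through the haemolysis sample, central-laboratory Hb through the haematology panel, and potassium through the chemistry panel.

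**Working it through.** The plan contains no figure to reproduce: no sample size calculation, SD, effect size or within-day bilirubin variation. The check is mainly textual, followed by an illustration on stated assumptions.

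**1. Which visits are affected.** Haemolysis markers are not sampled at V1. V2 is outside the permission. No dose is given at V7. That leaves V3 to V6, including the primary time point.

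**2. Whether a pre-dose draw already takes place.** Table 1, footnote 13, has "Iron-related parameters/markers of erythropoiesis sampled at pre-dose and 2 hours post-morning dose include total serum iron", and Sections 8.3 to 8.6 each list both iron draws. Section 8.8 keeps the pre-dose one mandatory. Blood is therefore already drawn before the dose at every affected visit. The second iron draw, 2 hours after the dose, is an obvious slot for a site that uses the permission. Section 2.3.2 describes that time as close to the plasma peak.

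**3. Whether the SAP could detect a mixture.** It has no flag, timing rule or timing sensitivity analysis for these markers. A pre-dose and a post-dose value from the same day would be averaged. By contrast, SAP Section 5.8.3 summarises ECGs separately for the pre-dose and 2-hour time points.

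**4. Size, with the shift *d* assumed.** Allocation of 24 in the ratio 3:3:3:2:1 gives 6, 6, 6, 4 and 2, with placebo pooled to 6. If *k* of *n* Visit 6 samples are post-dose and each is shifted by *d* (in SDs of the change), the group mean change moves by (*k*/*n*) × *d*. With *n* = 6:

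| *d* (SD) | 1 of 6 post-dose | 3 of 6 | 6 of 6 |
|---|---|---|---|
| 0.10 | 0.02 | 0.05 | 0.10 |
| 0.25 | 0.04 | 0.13 | 0.25 |
| 0.50 | 0.08 | 0.25 | 0.50 |
| 1.00 | 0.17 | 0.50 | 1.00 |

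For comparison, the 95% CI half-width at *n* = 6 is t(0.975, 5)/√6 = 1.05 SD.

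**5. Added noise.** A mixture with post-dose share *p* = *k*/*n* inflates the SD by √(1 + *p*(1 − *p*)*d*²). At *p* = 0.5 this is 1.03 for *d* = 0.5 and 1.12 for *d* = 1.0.

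**6. Chance imbalance between arms.** Suppose each sample is post-dose independently with probability 0.25 to 0.5. Two arms of 6 then differ by at least two post-dose samples with probability 0.31 (at 0.25) to 0.39 (at 0.5). A difference of two moves the between-arm contrast by (2/6) × *d* = 0.33*d*. Independence is a reasonable approximation if timing is a site habit, because 24 subjects over about 20 sites is 24/20 = 1.2 per site.

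**7. After the change.** With *k* = 0 in every arm, the shift and the added noise from post-dose sampling are both zero.

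**The case against.** The strongest reply is that no mechanism is documented. The acute post-dose changes reported for the drug concern serum iron, TSAT and hepcidin (Protocol Section 1.4.1). Section 2.2 treats plasma iron as the acute marker and red-cell indices as the chronic one. Section 8.8 protects the acute measures (iron, PK, ECG, vital signs) and relaxes slower ones, which looks deliberate. This is fair for red-cell indices. Section 2.2 does not classify bilirubin either way, so it neither shows an effect nor excludes one.

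Second, the rule is the same in all cohorts, placebo subjects also take a morning dose, and sites are blinded. A non-drug timing effect is therefore non-differential between arms in expectation. This stands, but it does not remove the effect from the within-group change, nor chance imbalance in arms of six.

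Third, all analyses are descriptive, with no test or decision rule (SAP Sections 3.1 and 3.2), and the interval is wide compared with any plausible shift. This stands, and it limits the weight of the point.

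A reader might also infer that baseline is always a fasting morning sample, so that time-of-day and meal effects are confined to follow-up. The documents do not support this. The meal rule governs when the dose is taken, and Section 8.2 allows V2 to be attended the day before randomisation. Only a direct post-dose effect is confined to on-treatment visits.

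**Conclusion.** The point holds as an avoidable inconsistency on the sample that carries the primary endpoint. Section 8.8 departs from Table 1, Sections 8.3 to 8.6 and the SAP's own schedule, and the SAP could neither detect nor handle mixed timing.

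The documents do not establish the size, direction or frequency of any effect. The table above rests entirely on an assumed shift and an assumed number of post-dose samples. On those assumptions the effect is small to moderate beside the 1.05 SD half-width, except where the shift is large and most of an arm is sampled post-dose.

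Three stronger readings should be resisted:
- **That the results are biased.** Section 8.8 is permissive, and nothing shows that post-dose sampling occurred.
- **That the shift can be judged against the 20% reduction criterion in SAP Section 5.7.3.** That criterion applies to each subject in an exploratory summary, whereas the shift here is in an arm mean.
- **That the flexibility serves no purpose.** Section 8.8 gives flexibility as its reason. The documents show only that a pre-dose draw is already required.

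The change is worth making because it is inexpensive and removes a source of doubt about the primary endpoint. The point does not invalidate the analysis.

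**What to change.** **Protocol.** In Section 8.8, move the haemolysis-marker sample, and the haematology and serum chemistry samples that carry central Hb and potassium, from the post-dose list to the must-be-pre-dose list, to be drawn with the pre-dose iron sample. This brings Section 8.8 into line with Table 1, Sections 8.3 to 8.6 and SAP Table 3. It needs no extra visit or venepuncture. It costs sites a little flexibility and requires a protocol amendment with authority and ethics approval (Section 16.2), across the planned 5 or more countries.

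**SAP, for samples already collected.** SAP V2.0 describes missing indirect bilirubin already seen at baseline and Visit 6, so part of the sampling is past. Where draw and dose times are recorded:
- classify each post-baseline haemolysis sample as pre-dose or post-dose;
- report the counts by arm and visit;
- in Section 5.1.3, do not average pre-dose and post-dose values from the same day;
- add to Section 5.7.1 a pre-dose-only sensitivity summary of the primary endpoint.

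This costs one flag and one extra summary. Feasibility is not assured: the protocol explicitly requires the dose time in the eCRF only for the first dose, and the eCRF and laboratory manual are not among the documents. If timing cannot be recovered, the study report should say so and should not describe the samples as uniformly trough.

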8.9 Allowed Adaptations in Case of Extraordinary Events, e.g., COVID-19

Extraordinary events may call for specific measures to maintain subject safety and guarantee conduct of clinical investigations according to established general and specific guidelines and regulations to meet agreed regulatory, quality, and scientific expectations.

For this, the following adaptations are considered for specific situations:

- Site visits are not possible within the defined time window, possibly leading to delayed:
 - Physical examination: consultation by local physician, follow-up assessment and guidance on drug adaptations via phone, remote visits at subject's home (e.g., home nursing)
 - Laboratory assessments: consultation by local physician, visit at local laboratory for blood analysis, or via home nursing
 - Adaptation of IMP: dispense sufficient amount of IMP at previous visit, delivery to subject's home by qualified designee as assigned by the Principal Investigator, or consider handover of IMP to relatives if allowed and in compliance with the applicable International Council for Harmonisation (ICH) Good Clinical Practice and other applicable laws and regulations, phone call by treating physician to guide dose adaptation of drugs
 - On-site monitoring: accept delayed on-site monitoring, conduct remote monitoring
 - On-site auditing: accept delayed on-site auditing, conduct remote auditing
 - AE/SAE/special situation reporting: frequent phone call visits
- Site visits are not possible within the defined time window, possibly leading to no:
 - Physical examination: consultation by local physician, follow-up clinical assessment via phone remote visits at subject's home (e.g., home nursing)
 - Laboratory assessments: consultation by local physician, local laboratory for blood analysis, or via home nursing
 - Adaptation of IMP: dispense sufficient amount of IMP at previous visit, delivery to subject's home by qualified designee as assigned by the Principal Investigator, or consider handover of IMP to relatives if allowed and in compliance with the applicable ICH Good Clinical Practice and other applicable laws and regulations, phone call by treating physician to guide dose adaptation of drugs

- On-site monitoring: accept delayed on-site monitoring, conduct remote monitoring
- On-site auditing: accept delayed on-site auditing, conduct remote auditing
- AE/SAE/special situation reporting: frequent phone call visits

